#### 7.3. Handling of Values Below (or Above) a Threshold

Except for **the**, values below (above) the detection limit will be imputed by the value one unit smaller or larger than the detection limit itself. In listings, the original value will be presented.

Example: if the database contains the value "<0.04", then for the descriptive statistics the value "0.03" will be used. The value ">1000" will be imputed by "1001".

For data, values below the detection limit will be imputed by zero.

#### 7.4. Handling of Missing Data

#### 7.4.1. Primary Approach

As the primary approach, there will be no imputation of missing values and missing values will be excluded from analyses and data is assumed to be missing at random (MAR). Missing data resulting from stopping the study is assumed to be missing completely at random (MCAR).

Missing data/visits due to the study conduct being affected by the COVID-19 pandemic (e.g. lockdown rules) can be considered MAR.

# 7.4.2. Handling of Missing Date Time Data

No imputations will be done in case of missing date (time) fields, nor for the missing parts of partially known date (time) fields.

Assessments with missing date (time) will be omitted from the analysis.

Event-type data (e.g. adverse events, concomitant medications) with missing date (time) will be allocated to analysis periods using a worst-case approach as explained in the respective sections.

# 7.4.3. Sensitivity Analyses

Since no treatment effect was observed and the study was stopped for lack of efficacy, sensitivity analyses to investigate the robustness of results will be limited. Description of sensitivity analyses are kept as documented in the original SAP for reference but most of them will not be performed (details in sections 9.1 and 9.3.2.2)

Several sensitivity analyses will be performed to investigate the impact of missing data, including analyses assuming missing not at random (MNAR), of protocol deviations, early study termination and treatment interruptions or discontinuation as well as changes in standard of care. Details are in the relevant efficacy sections below.

# 7.5. Handling of Outliers

All measured values will be included in the analyses. Extreme outliers will be evaluated before unblinding and if needed, additional sensitivity analyses will be added.

# 7.6. Stratification Factors

The analyses will be stratified by the type of standard of care taken at randomization: nintedanib, pirfenidone or neither. In all analyses, except if indicated otherwise, the stratum will be the SOC at randomization and will not change if the subject switches SOC during the study.

In case there is a discrepancy in the stratification reported in interactive web response system (IWRS) versus in the eCRF, then the stratum reported in the eCRF will be used in analyses, and the discrepancy will be flagged in the appropriate listing.

# 7.7. Exclusion of Data in Case of Quality Issues

In case of serious breach or other site-related quality concerns the study team in collaboration with the quality department will assess the impact on the data and may decide to exclude the data from analyses, this will be documented in the eTMF.

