# **VERSION HISTORY**

SAP Amendment #	Date	Description of changes
SAP Version 1.0	13/02/2019	First version
SAP Version 2.0	25/25/2021	
 
Changes to planned analysis due to termination GLPG1690- CL-303/304 program (text in Italic font will not be performed)
 
Addition Section 7.7: exclusion of data in case of quality issues.
 
Section 9.2.7: addition more details on standard of care analyses
 
Section 9.4.2.5: Scoring based on CTCAE/Other Gradings: updated in agreement with clinicians
 
Addition COVID-19 analyses
 
Changes to CSP sections due to amendments CSP
 
General editorial changes to improve wording
 

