# 1. INTRODUCTION

This statistical analysis plan (SAP) describes the analyses for each of the GLPG1690-CL-303 and GLPG1690-CL-304 final analyses for the clinical study reports (CSR). Since the studies are identically designed, only one SAP is covering both CSRs.

A decision was taken to halt the ISABELA Phase 3 clinical studies (study numbers GLPG1690-CL-303 and GLPG1690-CL-304) with the investigational autotaxin inhibitor ziritaxestat (GLPG1690) in patients with idiopathic pulmonary fibrosis. The decision was based on the recommendations of the Independent Data Monitoring Committee (IDMC) which, following a regular review of unblinded data on February 9, concluded that ziritaxestat's benefit-risk profile no longer supported continuing these studies.

In view of the above, no market authorisation application will be submitted for ziritaxtestat for the treatment of IPF. Therefore, it was decided to limit the analyses to the primary, key secondary and safety endpoints and any analyses important to better understand the reason for the results seen, or relevant for scientific knowledge for future compounds. Since no treatment effect was observed and the study was stopped for lack of efficacy, sensitivity analyses to investigate the robustness of results will also be limited.

The results will be presented in an abbreviated CSR.

All descriptions as documented in the original SAP were kept for reference, but endpoints and analyses deemed not applicable for the abbreviated CSR are in *Italic font*, and will not be included for the final analysis. A list of the analyses that will not be performed can be found in section 9.1.

Analyses on the pooled data from both studies for the integrated summaries of efficacy and safety were planned to be very similar (adjusted for study as appropriate) and to be detailed in a separate pooled-analysis SAP. As no market authorisation application will be submitted, these pooled analyses will not be performed and the pooled-analysis SAP will not be written.

Technical details on derivations and mock tables, listings and figures will be presented in a separate document.

A separate SAP will be written for the population pharmacokinetics (PK ) analyses.

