#### 2.7. Randomization and Blinding

Details on randomization and blinding are in Section 4.6 of the study protocols.

An independent data monitoring committee (IDMC) will monitor the safety of the subjects in the study on a regular basis and will also assess the effect of treatment with GLPG1690 on lung function as assessed by rate of decline in FVC to evaluate the risk-benefit. In addition, an interim analysis to assess futility will therefore be performed when a reasonable number of subjects have completed 52 weeks of treatment (e.g. at least 25% subjects from the two studies combined) (see Section 7.3.2 of the CSP). The results will be reviewed by the IDMC, who will then make a recommendation to the sponsor on the progress of the study. Specific details on timing of the analyses, futility criteria, and statistical analyses to be performed will be detailed in the IDMC charter or SAP, as appropriate. To allow collection of as much safety information as possible on a potential down-titration dose, a futile dose will continue if the other dose does not show futility. Either the study will continue as planned or both doses (and the study) will be terminated. Sponsor personnel will remain blinded and the study will not be stopped for a beneficial effect. The IDMC and statistical support group reporting to the IDMC will be unblinded, but they are independent of the study team. Sponsor personnel will remain blinded.

After it was decided to terminate the trial, part of the study team was unblinded in order to be able to investigate the findings.

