# 3.3. Full Analysis Set (FAS)

All randomized subjects who received at least one dose of IP.

All data will be included irrespective of IP interruption or termination and changes in standard of care. Only efficacy data after lung transplant will be excluded.

If a subject is unblinded (e.g. in case of a serious adverse event [SAE]), all data of this subject recorded in the database will be included in the analyses.

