#### 9.4.1.6.4. Adverse Events Related to Nintedanib or Pirfenidone

To investigate the events expected to be associated with pirfenidone and nintedanib, Kaplan-Meier curve and table, as well as a counts table by system organ class and preferred term, by treatment, as well as by stratum and treatment will be provided for the preferred terms of events of specific interest to nintedanib (e.g. diarrhea, nausea, vomiting, dehydration, weight decrease and decreased appetite adverse events) and pirfenidone (e.g. photosensitivity reactions, nausea, diarrhea, dyspepsia, vomiting, gastro-esophageal reflux disease, and abdominal pain). The full list of preferred terms to be investigated will be detailed before unblinding for the CSR.

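### SAP 7.7, added once the efficacy outcome was known, lets site data be excluded without a blinded decision, a deadline before lock, or an analysis that keeps the data in

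*SAP*

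**What the plan says.** The SAP version history lists "Addition Section 7.7: exclusion of data in case of quality issues" among the changes in version 2.0, the version revised because the programme was terminated. Section 7.7 itself provides that, after a serious breach or another site-related quality concern, the study team, together with the quality department, judges the impact and then "may decide to exclude the data from analyses, this will be documented in the eTMF". The record it names is the eTMF.

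The same version shows what was known at the time. Its Introduction explains why the robustness checks are cut back: "Since no treatment effect was observed and the study was stopped for lack of efficacy, sensitivity analyses to investigate the robustness of results will also" (the sentence ends by restricting them). Section 2.7 adds: "After it was decided to terminate the trial, part of the study team was unblinded in order to be able to investigate the findings".

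The inclusion rule in section 3.3 (Full Analysis Set, FAS) reads "All data will be included irrespective of IP interruption or termination and changes in standard of care", and its next sentence names efficacy data after lung transplant as the sole exclusion. Section 7.7 is not mentioned there.

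Section 3.4, on the per-protocol set (no longer to be analysed), required the deviations leading to exclusion to be settled before unblinding and before database lock. Protocol section 7 puts the same timing on the assessment of protocol deviations.

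**The concern.** Removing data from a site with a serious breach can be right. What protects such a decision is that the people making it cannot see which way it moves the result, and that a reader can see the result both ways. Section 7.7 requires neither. It gives the decision to the study team without separating the members who were unblinded, and it entered the plan in a version that already states the efficacy outcome.

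The rule speaks of analyses without limit, so it covers the primary FVC slope, the key secondary endpoints, mortality and safety. The CSR is meant to explain why the programme failed and to inform work on future compounds. Its mortality and safety estimates should therefore be traceable to all treated subjects, or to a visibly justified subset.

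**Working it through.** The point rests on the text, so the sections are compared first. The arithmetic afterwards is illustration only.

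**Comparison of rules**

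| Question | Per-protocol exclusions (SAP 3.4) | Site-quality exclusions (SAP 7.7) |
|---|---|---|
| Decided before unblinding? | Yes | Not stated; part of the team was already unblinded (2.7) |
| Decided before database lock? | Yes | Not stated |
| Analyses affected | A sensitivity analysis | Any analysis, including the primary |
| Result with the data kept in? | Yes, the FAS analysis | None planned |

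**Do the retained sensitivity analyses restore excluded sites?** Under 9.1 and 9.3.2.2, two remain for the primary endpoint: the MMRM (9.3.2.2.1) and the slope model on all study data (9.3.2.2.5). In the second, all data means follow-up beyond Week 52, not all sites. Neither brings back data removed under 7.7.

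**Would the CSR show the exclusion?**
- Section 9.1 sends changes made after unblinding to the CSR with a reason. An exclusion under 7.7 is arguably the plan being applied, not changed.
- Section 9.2.3 lists subjects excluded from analysis sets. Section 7.7 removes data from analyses, while the FAS definition stays the same, so such data need not appear in that listing.
- Section 9.1 drops the tabulation of subjects per analysis population.

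Transparency is therefore partial.

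**The plan's own figure.** Inputs from protocol 7.1: SD 275 mL, 250 per arm, 80 mL for 600 mg, two-sided alpha 4% for 600 mg and 1% for 200 mg.
- SE = 275 × √(2/250) = 24.6 mL.
- Power for 600 mg alone = Φ(80/24.6 − 2.054) = Φ(1.20) = 88.5%.
- Power for at least one dose, with effects 80 and 0 mL and correlation 0.5 from the shared placebo arm: 88.8%. Protocol Table 2 states 88.8%, so the design figure is reproduced.

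**Illustrations.** The excluded shares, the gap and the number of candidate sites are assumptions; none is in the documents.

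1. Loss of precision if a share f is removed evenly across arms, with n = 250(1 − f):
   - f = 2%: n = 245, SE 24.85 mL, power 87.8%
   - f = 5%: n = 237.5, SE 25.24 mL, power 86.8%
   - f = 10%: n = 225, SE 25.93 mL, power 84.9%
2. Shift in the estimate = −f/(1 − f) × gap, where the gap is the excluded sites' treatment difference minus the all-data estimate. For a gap of 100 mL:
   - f = 2%: −0.02/0.98 × 100 = −2.0 mL
   - f = 5%: −0.05/0.95 × 100 = −5.3 mL
   - f = 10%: −0.10/0.90 × 100 = −11.1 mL
3. Type I error for 600 mg (nominal 4%) if the more extreme of the all-data result and any result with one candidate site dropped were reported. Simulated under no effect, 400,000 replicates:
   - 1 candidate site with 2% of subjects: about 4.5%
   - 1 site with 5%: about 4.9%
   - 5 sites with 2% each: about 5.8%
   - 5 sites with 5% each: about 7.0%

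**The case against.** The strongest defence is that 7.7 is an ordinary data-integrity clause. It needs a site-level trigger, an impact assessment and the quality department. Only part of the team was unblinded, and for another purpose: "part of the study team was unblinded in order to be able to investigate the findings". Sections 9.1 and 9.2.3 give some visibility in the CSR. The studies were stopped, no marketing application will follow, and only abbreviated reports are planned. Forcing data from a site in serious breach into the main analysis could also do harm. All of this stands, and it limits the weight of the point and shapes the fix. It does not supply a blinded decision or a result with the data kept in.

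A reader might infer more than the documents support:

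- **That unblinded members take the decision, or that data were dropped.** Neither is stated. The date of version 2.0 is printed as 25/25/2021, so its timing relative to lock cannot be fixed either.
- **That 7.7 contradicts section 7.5, which keeps all measured values.** Section 7.5 concerns outliers, and 9.3.2 already removes post-bronchodilator and unacceptable spirometry by stated rule. The real mismatch is with the sole-exclusion sentence in 3.3.
- **That other choices due before unblinding carry the same risk.** Section 9.4.1.6.4 says "The full list of preferred terms to be investigated will be detailed before unblinding for the CSR", and 9.2.5.3 defers the definition of respiratory medications to a separate document. These govern adverse-event displays and medication tables, cannot move the primary result, and are not shown to be still open.
- **That the possible bias is unbounded.** The trigger is site quality, and nothing in 7.7 provides for removal by arm.

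**Conclusion.** The point holds as a gap in safeguards. As written, 7.7 permits an exclusion decided with knowledge of outcome or treatment codes, at any time, with no all-data result beside it. That is weaker than the SAP's own standard for per-protocol exclusions, although its reach is wider. It is an open route, not shown bias.

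Its size cannot be derived from the documents. On the assumptions above, the primary estimate would move by single millilitres up to about 11 mL, against an SE of 24.6 mL, and the nominal 4% error would rise to between about 4.5% and 7.0%. The error figures matter less now that the outcome is known and no application is planned. The visibility of mortality and safety results is the more practical reason to act. The change should be made, because the gap affects the main analyses and closing it costs little.

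**What to change.** 1. State in 7.7 that exclusions are decided before database lock, by named roles with no access to treatment codes or by-arm results.
2. Whenever data are excluded, report the primary, key secondary and mortality analyses both with and without them. If the decision could not be made blinded, make the all-FAS result the main one.
3. List in the CSR the excluded sites, the number of subjects per arm and the reasons.
4. Cross-reference 7.7 in section 3.3, so that the FAS rule and the exclusion rule agree.

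The cost is SAP wording, a few model reruns and possibly a short delay to identify blinded decision makers. Where a blinded decision is no longer possible, there is a real trade-off: unreliable data may sit in the main analysis. Showing the result without them alongside lets a reader judge that.

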# 8. INTERIM ANALYSES AND DATA MONITORING COMMITTEE REVIEW

To protect the safety of the subjects in the study and integrity of the study data, an IDMC will be implemented.

In parallel to assessing potential safety risks on a regular basis, the IDMC will also examine the effect of treatment with GLPG1690 on lung function as assessed by rate of decline in FVC using the data from the identically designed studies GLPG1690-CL-303 and GLPG1690-CL-304. An interim analysis to assess futility will be performed when a reasonable number of subjects have completed 52 weeks of treatment (at least 25% subjects completing Week 52 or 70% information available, whichever comes latest, the exact timing will be determined based on the actual recruitment). The results will be reviewed by the IDMC, who will then make a recommendation to the sponsor on the progress of the study. The Sponsor will remain blinded to treatment allocations and results of the analyses. To allow collection of as much safety information as possible on a potential down-titration dose, a futile dose will continue if the other dose does not show futility. Either the study will continue as planned or both doses (and the study) will be terminated. Specific details on timing of the analyses, futility criteria, and statistical analyses to be performed will be detailed in the IDMC charter and SAP, as appropriate. A summary of the futility approach is also provided in Appendix 5.

Given there is no plan to terminate the study early for overwhelming efficacy results, no adjustment of the alpha level is considered needed.

No other interim analyses are planned for these studies.

# 9. STATISTICAL ANALYSES

#### 9.1. Changes to the Planned Analyses, Not Covered by Protocol Amendments

In view of the termination of the ISABELA studies and the decision to write an abbreviated CSR, it was decided to limit the analyses to the primary, key secondary and safety endpoints and any analyses important to better understand the reason for the results seen, or relevant for scientific knowledge for future compounds. Since no treatment effect was observed and the study was stopped for lack of efficacy, sensitivity analyses to investigate the robustness of results will also be limited.

A detailed list of the analyses that will not be performed can be found in the table below. In the remainder of the document the descriptions as documented in the original SAP are kept for reference; but analyses that will not be performed are in *Italic font*.

Section SAP	Analyses to be omitted
9.2.1	
 
Baseline EQ_5D
 
Baseline LCQ total score and domains
 
Baseline K-BILD total score and domains
 
Baseline VAS Cough and Urge to Cough
 

	
 
Baseline SpO2 during 6MWT (%)
 
Frequency tabulation baseline Physical examinations
 

9.2.2	
 
The number (percent) of subjects in the different analysis populations
 
The number (percent) of subjects per analysis window as defined in Section 6.3 for analysis.
 

	
 
Descriptive statistics of the duration of the analysis periods
 
Number of subjects with a deviation of more than the number of days allowed per protocol from the target of the analysis windows, per window.
 
Descriptive statistics of the number of days distance from the target of
 

	the window, as specified in the protocol, as well as of the relative day per window. These will allow to assess if the later visits (especially the close-out visits) are done close to scheduled visits.
9.2.3	All major protocol deviations will be tabulated, not only the ones impacting efficacy, as this assessment will not be done. A list of all major protocol deviations will be provided without the flag for impacting efficacy.
9.2.5.3	Analyses restricted to medications taken up to 30 days after the last dose of IP.
9.2.6	Analyses on exposure and compliance parameters on data up to 52 weeks
9.2.7	KM analyses for time to first switch in standard of care
9.3.1	Pooled analyses will not be performed.
9.3.2.2	
 
9.3.2.2.2 Per protocol analysis
 
9.3.2.2.3 On-treatment
 
9.3.2.2.4 After Lung Transplant
 
9.3.2.2.6 Completers vs Non-completers
 
9.3.2.2.7 Impact of missing data – Pattern mixture
 
9.3.2.2.8 Impact of SOC
 

9.3.3	-On-treatment analysis -Negative binomial model
9.3.5	-Per protocol analysis -Random coefficient regression model

9.3.6	9.3.6.1 EQ_5D 9.3.6.2 LCQ 9.3.6.3 K-BILD
	9.3.6.3 VAS Cough and Urge to Cough
9.3.7	Functional Exercise Capacity and it is all analyses omitted, except for total distance walked in 6 minutes, this parameter will be analyzed.
9.3.9	- No subject profiles will be created.
9.3.10	No analyses per age, sex, race and per geographical region will be done.
9.3.11	
9.4.5	Physical examinations frequency table
9.4.3.6	
 
Tabulation of ECG interpretations
 
Table summarizing the pre- and postdose values at these selected visits.
 

Tables and listings to investigate the impact of COVID-19 on the study have been added.

If changes are needed after unblinding, these will be documented in the CSR with an explanation for the reason for the change.

#### 9.2. Subject Information

Subject information will be tabulated using the FAS population. No inferential testing will be performed nor will p-values be provided.

#### 9.2.1. Demographic and Baseline Disease Characteristics

Demographic and baseline disease characteristics will be tabulated with descriptive statistics per treatment group and for all subjects pooled. The same summaries will also be provided by stratum. The following parameters will be summarized:

- Stratum: standard of care (pirfenidone, nintedanib or neither)
- Sex
- Age at the moment of signing the ICF (years) as recorded in the database
- Age categories:
  - $\geq 18 <65$  years
  - $\geq 65 85$  years
  - $\geq$  85 years
- Race

- Ethnicity
- Height at baseline (cm)
- Weight at baseline (kg)
- Body mass index (BMI) at baseline  $(kg/m^2) = \frac{weight (kg)}{height^2 (m^2)}$
- BMI at baseline, categorized:
  - $\leq 18.5 \text{ kg/m}^2$
  - $>18.5 \le 25.0 \text{ kg/m}^2$
  - $>25.0- \le 30.0 \text{ kg/m}^2$
  - $> 30.0 \text{ kg/m}^2$
- Systolic and diastolic blood pressure (mmHg), heart rate (beats/min), respiratory rate (breaths/min) and oxygen saturation (%) at baseline
- Alcohol status: never, current, former
- Smoking status: never, current, former
- Duration of IPF (years) = (date of first intake of IP date of initial diagnosis)/365.25. If the date of initial diagnosis is incomplete, then the following rules will be applied: Missing day: use the first day of the month. Missing month: use January.
- Duration of IPF, categorized as:
  - <0.5 year
  - $\geq 0.5 <1$  year
  - $\geq 1 < 2$  year
  - $\geq 2$  year
- Baseline spirometry values:
  - forced vital capacity (FVC) (mL),
  - percent predicted FVC (%),
  - forced expiratory volume in 1 second (FEV1) (mL),
  - percent predicted FEV1 (%),
  - FEV1/FVC ratio,
  - forced expiratory flow between 25% and 75% of exhaled volume (FEF25-75) (mL/s).
- Other baseline efficacy measures:
  - SGRQ total score and domains:
    - symptoms (assessing the frequency and severity of respiratory symptoms),
    - activity (assessing the effects of breathlessness on mobility and physical activity),
    - impact
  - *EQ-5D*,
  - LCQ total score and domains,
  - K-BILD total score and domains,
  - VAS Cough and Urge to Cough,
  - 6MWT distance,
- •
- SpO2 during 6MWT (%)
- DLCO (corrected for Hb)

A frequency tabulation per system organ class and treatment group (and overall) of the baseline physical exam results, categorized as normal/abnormal will also be provided.

